5.1 Inclusion Criteria

To be included in the study, each individual must satisfy all of the following criteria:

- 1. Male or female adults who have reached the age of consent in the applicable region (eg, ≥ 18 years in the US)
- 2. Written informed consent and any locally required authorization (eg, data privacy) obtained from the subject prior to performing any protocol-related procedures, including screening evaluations.
- 3. Clinical diagnosis of IgG4-RD.
- 4. Fulfillment of the 2019 ACR/EULAR classification criteria as determined by the Eligibility Committee. Specifically, subjects must meet the classification criteria entry requirements (including involvement of one of the following organs: pancreas, bile ducts/biliary tree, orbits, lungs, kidneys, lacrimal glands, major salivary glands, retroperitoneum, aorta, pachymeninges, or thyroid gland [Riedel's thyroiditis]), must not meet any of the classification criteria exclusions, and must achieve at least 20 classification criteria inclusion points.
- 5. Experiencing (or recently experienced) an IgG4-RD flare that requires initiation or continuation of GC treatment at the time of informed consent. This criterion may be met in two ways:
 - On GC therapy for recent IgG4-RD flare, having received a maximum of 4 weeks of treatment prior to informed consent at a dose no higher than 60 mg/day prednisone or equivalent, and at 20 mg/day prednisone or equivalent on the day prior to randomization, or
 - Experiencing active disease not currently being treated at the time of informed consent, with planned initiation of treatment for flare with GC at a maximum dose of 60 mg/day prednisone (or equivalent) and with a plan to be treated at a dose of 20 mg/day of prednisone (or equivalent) on the day prior to randomization, for a total duration of GC treatment during screening period of at least 3 weeks at the time of randomization.

This GC therapy can either be newly initiated or be increased from a maintenance dose of ≤ 10 mg/day of prednisone or equivalent.

Subjects unable to be tapered to 20 mg/day of prednisone or equivalent by Visit 2 may not be randomized.

Total duration of GC treatment must be at least 3 weeks and not exceed 8 weeks prior to randomization.

- 6. IgG4-RD affecting at least 2 organs/sites at any time in the course of IgG4-RD with documentation to confirm. One organ must meet the requirements for the ACR/EULAR classification criteria (inclusion 4); the second organ is as defined by the investigator.
- 7. Willing and able to comply with the protocol, complete study assessments, and complete the study period.
- 8. Non-sterilized male subjects who are sexually active with a female partner of childbearing potential must use a condom with spermicide (where spermicide is available) from Day 1 through to the end of the study and must agree to continue using such precautions for at least 6 months after the final dose of IP.

Females of childbearing potential must have a negative serum pregnancy test at screening. Females of childbearing potential who are sexually active with a non-sterilized male partner must use a highly effective method of contraception (Table 2) from signing informed consent and must agree to continue using such precautions through the end of the follow-up of the study and at least 180 days after the last dose of IP; cessation of contraception after this point should be discussed with a responsible physician. Periodic abstinence, the rhythm method, and the withdrawal method are not acceptable methods of contraception. A recommendation will be made that the female partners (of childbearing potential) of male study participants should use a highly effective method of contraception other than a barrier method.

Females of childbearing potential are defined as those who are not surgically sterile (ie, surgical sterilization includes bilateral tubal ligation, bilateral oophorectomy, or hysterectomy) or those who are not postmenopausal (defined as 12 months with no menses without an alternative medical cause and a follicle-stimulating hormone within the postmenopausal range as established by the clinical laboratory).

Table 2Highly Effective Methods of Contraception for Females of Childbearing
Potential

Physical Methods	Hormonal Methods
 Intrauterine device (IUD) Intrauterine hormone-releasing system (IUS) ^a 	• Combined (estrogen and progestogen-containing hormonal contraception)
 Bilateral tubal occlusion Vasectomized partner^b 	Oral (combined pill)Injectable
 Sexual abstinence ° 	• Transdermal (patch)
	 Progestogen-only hormonal contraception associated with inhibition of ovulation^d
	• Implantable
	• Intravaginal

a This is also considered to be a hormonal method.

b With appropriate post-vasectomy documentation of surgical success (absence of sperm in ejaculate).

- c Sexual abstinence is considered to be a highly effective method only if defined as refraining from heterosexual intercourse during the entire period of the study and if it is the preferred and usual lifestyle of the subject.
- d Progestogen-only hormonal contraception, where inhibition of ovulation is not the primary mode of action (minipill) is not accepted as a highly effective method.

5.2 Exclusion Criteria

Any of the following excludes an individual from participation in the study:

- 1. Severe cardiovascular, respiratory, endocrine, gastrointestinal, hematological, neurological, psychiatric, or systemic disorder, or any other condition that, in the opinion of the Investigator, would place the patient at unacceptable risk of complications, interfere with evaluation of the IP, or confound the interpretation of patient safety or study results.
- 2. History of solid organ or cell-based transplantation.
- 3. Known immunodeficiency disorder.

- 4. Active malignancy or history of malignancy that was active within the last 10 years, except as follows:
 - In situ carcinoma of the cervix following apparently curative therapy > 12 months prior to screening,
 - Cutaneous basal cell or squamous cell carcinoma following apparently curative therapy,
 - Prostate cancer treated with radical prostatectomy or radiation therapy with curative intent > 3 years prior to screening and without known recurrence or current treatment, or
 - Thyroid cancer for which surgery has been performed and there is no evidence of active disease.
- 5. Receipt of any biologic B cell-depleting therapy (eg, rituximab, ocrelizumab, obinutuzumab, ofatumumab, inebilizumab) in the 6 months prior to screening.
- 6. Receipt of non-depleting B-cell-directed therapy (eg, belimumab), abatacept, or other biologic immunomodulatory agent within 6 months prior screening.
- 7. Receipt of non-biologic DMARD or immunosuppressive agent other than GCs (eg, azathioprine, mycophenolate mofetil, methotrexate, others) within 4 weeks prior to screening.
- 8. Receipt of any investigational agent < 12 weeks or < 5 half-lives of the drug (whichever is longer) prior to screening.
- 9. Inability to be tapered off of GC therapy by 8 weeks post-randomization (other than ≤ 2.5 mg/day prednisone or equivalent for treatment of adrenal insufficiency or intolerance of taper) in the opinion of the Investigator.
- 10. Receipt of live vaccine or live therapeutic infectious agent within the 2 weeks prior to screening.
- 11. Pregnancy, lactation, or planning to become pregnant within 6 months of the last dose of IP.
- 12. Positive test for, or prior treatment for, hepatitis B or HIV infection. A positive test for hepatitis B is detection of either (1) hepatitis B surface antigen (HBsAg); or (2) hepatitis B core antibody (anti-HBc); and in Japan only (3) hepatitis B surface antibody (HBsAb)
- 13. History of untreated hepatitis C infection, or positive antibody test for hepatitis C virus (HCV) unless patient is considered to be cured following antiviral therapy and has a HCV viral load below the limit of detection at least 24 weeks after completion of treatment at site or central lab.
- 14. Evidence of active tuberculosis (TB) or being at high risk for TB based on:
 - History of active TB or untreated/incompletely treated latent TB. Patients with a history of active or latent TB who have documentation of completion of treatment according to local guidelines may be enrolled.
 - History of recent (≤ 12 weeks of screening) close contact with someone with active TB (close contact is defined as ≥ 4 hours/week OR living in the same household OR in a house where a person with active TB is a frequent visitor).
 - Signs or symptoms that could represent active TB by medical history or physical examination.

- Positive, indeterminate, or invalid interferon-gamma release assay test result at screening, unless previously treated for TB. Patients with an indeterminate test result can repeat the test once, but if the repeat test is also indeterminate, the patient is excluded.
- Chest radiograph, chest computed tomography (CT) or MRI scan that suggests a
 possible diagnosis of TB or suggests that a work-up for TB should be considered; all
 patients must have had lung imaging with an acceptable reading within 6 months
 prior to consent, or during screening.
- 15. History of > 1 episode of herpes zoster (any grade) and/or any other definite or probable opportunistic infection in the 12 months prior to screening (see Appendix A) for details on opportunistic infections that require exclusion).
- 16. Known history of allergy or reaction to any component of inebilizumab formulation or history of anaphylaxis to any human gamma globulin therapy.
- 17. Allergy to or intolerance of protocol-required treatment, including medications for prophylaxis of infusion reactions (antipyretic such as paracetamol/acetaminophen or equivalent, diphenhydramine or equivalent, and methylprednisolone or equivalent).
- Estimated glomerular filtration rate < 30 mL/min/1.73 m² by Modification of Diet in Renal Disease Study (MDRD) equation (NIDDK).
- 19. Blood tests at screening that meet any of the following criteria:
 - Hemoglobin < 7.5 g/dL
 - Neutrophils < 1200/mm3
 - Platelets $< 110 \times 109/L$
 - Eosinophil count > 3000/mm3
 - Prothrombin time > 1.2 x upper limit of normal (ULN); however, subjects who are anticoagulated due to atrial fibrillation and who have aspartate aminotransferase (AST) and alanine aminotransferase (ALT) levels ≤ 2 x ULN are not excluded
 - Total immunoglobulins < 600 mg/dL
 - CD19+ B cells at screen < 40 cells/ μ L; an exclusionary value may be repeated.
- 20. Subjects with the following abnormal liver function tests in the absence of hepatobiliary IgG4-RD activity:
 - Aspartate aminotransferase (AST) $> 2 \times ULN$
 - Alanine aminotransferase (ALT) $> 2 \times ULN$
 - Total bilirubin (TBL) > 2 × ULN unless AST, ALT, and hemoglobin are within central laboratory normal range and the patient has a known history of Gilbert syndrome

OR

Subjects with the following abnormal liver function tests in the presence of hepatobiliary IgG4-RD activity:

- AST > $10 \times ULN$
- ALT > $10 \times ULN$

- TBL > $5 \times ULN$
- Screening liver function tests may be repeated prior to randomization to permit abnormal values due to hepatobiliary IgG4-RD activity to respond to GC treatment.
- 21. Known positive anti-neutrophil cytoplasmic antibodies (ANCA) targeted against proteinase 3 or myeloperoxidase based on patient records.
- 22. History of alcohol or drug abuse that, in the opinion of the Investigator, might affect patient safety or compliance with visits or interfere with safety or other study assessments.
- 23. Active, clinically significant infection at the time of randomization (IP administration may be delayed until recovery, if within screening window, otherwise subject may be rescreened).
- 24. Participation in any clinical trial that includes use of any pharmacologic intervention.

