6.2 Schedules of Study Assessments

6.2.1 Schedule of Screening Assessments and Procedures

Table 3 summarizes the screening procedures for the study. All screening assessments must be completed within 28 days prior to randomization. In some cases, more than one screening visit may be required to complete all procedures. Safety laboratory tests may be repeated once during screening.

Study Period	Screening
Visit Number	V1
Study Day	Up to Day -28 ^a
Written informed consent and IXRS assignment of SID number	Х
Demographics	Х
Medical history	Х
Assessment of AEs and SAEs	Х
Review of vaccination history ^b	Х
Assessment of prior and concomitant medications	Х
Vital signs (temperature, pulse, respiration rate, and blood pressure)	Х
Height and weight	Х
Full physical examination excluding pelvic and rectal exam	Х
12-lead ECG	Х

Table 3Screening Assessments and Procedures

Table 3Screening Assessments and Procedures

Study Period	Screening				
Visit Number	V1				
Study Day	Up to Day -28 ^a				
CT or MRI scan (or equivalent) of chest, abdomen and pelvis at screen or during most recent active disease (ie, within prior 3 months), and, if head and neck disease, MRI (or equivalent) of affected area at screen or within prior 3 months. If clinically indicated, repeat imaging can be performed prior to randomization to assess response to glucocorticoids and to ensure exclusion of malignancy.	Х				
IgG4-RD RI score	Х				
Blood collection for:					
 Safety laboratory testing (serum chemistry ^c, hematology, and coagulation) Serum β-hCG pregnancy test (all females) Follicle-stimulating hormone (potentially postmenopausal females) Hepatitis B surface antigen, anti-HBc, and in Japan only HBsAb Hepatitis C testing: a) Hepatitis C Ab in patients not known to have had HCV b) HCV load in patients known to have completed curative HCV treatment at least 24 weeks prior to screening HIV-1 and HIV-2 testing IGRA testing for TB IgG4 level 	Х				
Urine collection for urinalysis (dipstick and, for abnormal dipstick, microscopic) and for urine protein/creatinine ratio	Х				
	1				
Verify preliminary eligibility based on data from Screening Visit prior to scheduling Visit 2	Х				

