Ab = antibody; AE = adverse event; β-hCG = serum human chorionic gonadotropin; CT = computed tomography; ECG = electrocardiogram; HCV = hepatitis C virus; Ig = immunoglobulin; IgG4-RD RI = IgG4-RD Responder Index; IGRA = interferon-gamma release assay; IXRS = interactive voice/web response system; JCV = John Cunningham virus; MRI = magnetic resonance imaging; SAE = serious adverse event; SID = subject identification; TB = tuberculosis; V1 = visit 1. SID = subject identification;					

a Screening may be conducted over multiple visits.

b Subjects should be advised to be up to date on vaccines in accordance with local recommendations prior to enrollment. Vaccines are optimally administered at least 4 weeks prior to dosing to permit development of immune response. Subjects who, on the advice of their physician, should delay Dose 1 for > 28 days to permit a 4-week post vaccine interval to occur should be screen-failed and may be rescreened.

c In patients who enroll with a hepatobiliary flare whose screening liver function test values do not meet eligibility criteria, liver function tests may be repeated (Exclusion 20). Subjects whose values do not fall below the exclusionary values upon repeat may not be randomized.

Clinical Study Protocol VIB0551.P3.S2 - MITIGATE Amendment 9.1, 08AUG2023

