6.3 Description of Study Assessments and Procedures

6.3.1 Screening Procedures

6.3.1.1 Informed Consent

Subjects officially enter the screening period following provision of informed consent.

All candidates for enrollment will sign an informed consent form (ICF) prior to any protocol-related procedures, including screening activities. Informed consent must be obtained by the Principal Investigator (PI) or a designee, such as an Investigator, with Institutional Review Board (IRB)/Independent Ethics Committee (IEC) approved qualifications. See Section 10.3 for additional details.

After signing the ICF, each subject will be assigned a subject identification (SID) number that will be used on all subject documentation. Numbers will be assigned in ascending, sequential order. This number will also correspond to the subject number entered on test materials. Rescreened patients will receive a new SID number. See Section 5.3 for limitations on rescreening.

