7.1.1.4 Investigational Product Dosing and Administration

Prior to each infusion in the RCP and OLP, the Investigator or other qualified medical personnel must confirm that none of the conditions requiring delay or discontinuation of IP administration are met (Section 6.4.1).

Premedication (from commercial supplies) with a corticosteroid (eg, methylprednisolone 100 mg IV or equivalent), an antihistamine (eg, diphenhydramine 25-50 mg orally or equivalent), and an anti-pyretic (eg, acetaminophen 500-650 mg orally or equivalent) will be administered approximately 30-60 minutes prior to each IP infusion.

Vital signs will be obtained prior to the start of each IP infusion. An experienced and qualified staff member will place the IV access.

The prepared solution will be administered IV via an infusion pump at an incrementally increasing rate through an IV line containing a sterile, low-protein binding 0.2 or 0.22 micron in-line filter according to the schedule in Table 8.

Table 8Infusion Rate for Investigational Product after Dilution in a 250 mL IV
Bag

Elapsed Time (minutes)	Infusion Rate (mL/hour)
0-30	42
31-60	125
61 to end of infusion	333

IV = intravenous.

Clinical Study Protocol	Horizon Therapeutics Ireland DAC
VIB0551.P3.S2 - MITIGATE	Inebilizumab
Amendment 9.1, 08AUG2023	IgG4-Related Disease

Unless an infusion reaction occurs resulting in discontinuation of infusion, the entire infusion bag contents must be administered and the tubing must be flushed with a volume of saline at least as large as that of the tubing to ensure complete delivery of the IP infused at a rate not to exceed 333 mL/hour.

After completion of the infusion, subjects will be observed for at least one hour.

Medically qualified personnel must be immediately available to respond to emergencies during administration of IP. Appropriate drugs and medical equipment to treat acute hypotensive, bronchoconstrictive, or anaphylactic reactions must be immediately available, and study personnel must be trained to recognize and treat these reactions. Additionally, appropriate drugs and medical equipment to treat IRRs must be immediately available, and study personnel must be trained to recognize and treat these reactions.

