7.5 Concomitant Medications and Treatments

Subjects should receive all medications, including treatments for IgG4-RD, that are considered by their physician to be necessary for their health and well-being.

The Sponsor recommends that Investigators ensure that all patients are up to date with required vaccinations prior to entry into the study.

7.5.1 **Prohibited Medications**

Patients must receive all treatments that are considered necessary for their health in the judgment of their physician(s). The following prohibited medications will require the discontinuation of IP, but subjects who receive prohibited medications must remain in the study through the final Week 52 RCP visit.

Generally, GC treatment for reasons other than new or worsening IgG4-RD activity is prohibited, but exceptions are described in Section 7.5.2 (GCs for uses other than IgG4-RD). The per-protocol limitations on dose and duration of GC treatment for IgG4-RD flare are described in Section 7.6. The Investigator must provide the indication for each use of GC or other immunosuppressive therapy.

Additional prohibited medications in the RCP and OLP include:

- Biologic or non-biologic immunosuppressive agents other than GCs, including but not limited to, azathioprine, mycophenolate mofetil, cyclosporine, methotrexate, leflunomide, cyclophosphamide, rituximab, etanercept, adalimumab, infliximab, certolizumab pegol, golimumab, abatacept, and tocilizumab.
- Live viral vaccines or live therapeutic infectious agents.

Receipt of prohibited medication requires discontinuation of IP as described in Section 6.4.1.

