9 STATISTICAL CONSIDERATIONS

9.1 General Considerations

The analyses with a treatment policy strategy will include all data captured during the 52-week RCP, defined as the period from Day 1 (Dosing) at Visit 2 to the conclusion of the scheduled last RCP visit at Visit 15 (Week 52), inclusive.

The analyses applying the while-on-treatment strategy will include all data captured while subjects are on treatment, defined as the period from Day 1 (Dosing) at Visit 2 and 6 months after the last treatment during the RCP, inclusive.

Summary data will be presented in tabular format by treatment group. Categorical data will be summarized by the number and percentage of subjects in each category. Continuous variables will be summarized by descriptive statistics, including N, mean, standard deviation, median, and range. Data listings will be sorted by treatment group and patient number. Additional details of statistical analyses will be described in the statistical analysis plan (SAP).

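### Four prior-therapy exclusions stop at screening and the prohibited list starts at Day 1, so live vaccines, DMARDs and biologics given only during screening meet no mandatory bar

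*Protocol*

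**What the plan says.** Protocol 5.2 sets four look-backs that all end at screening: 6 months for B-cell depleters (exclusion 5), 6 months for non-depleting and other biologics (exclusion 6), 4 weeks for non-biologic DMARDs and other non-GC immunosuppressants (exclusion 7), and 2 weeks for live products (exclusion 10: "Receipt of live vaccine or live therapeutic infectious agent within the 2 weeks prior to screening").

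Protocol 6.3.1.1 fixes the start of screening: "Subjects officially enter the screening period following provision of informed consent". Protocol 6.2.1 fixes its maximum length: "All screening assessments must be completed within 28 days prior to randomization".

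On-study restrictions are in Protocol 7.5.1. The list is introduced by "Additional prohibited medications in the RCP and OLP include" and covers non-GC immunosuppressants and "Live viral vaccines or live therapeutic infectious agents". Protocol 9.1 gives the RCP window as "defined as the period from Day 1 (Dosing) at Visit 2 to the conclusion of the scheduled last RCP visit".

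Before each infusion, Protocol 7.1.1.4 says site staff "must confirm that none of the conditions requiring delay or discontinuation of IP administration are met", with a reference to 6.4.1. Item 12 of 6.4.1 is receipt of a prohibited medication and refers back to 7.5.1.

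On vaccines, Table 3 footnote b advises a gap of at least 4 weeks before dosing so that an immune response can develop. Its screen-fail route covers "Subjects who, on the advice of their physician, should delay Dose 1 for > 28 days to permit a 4-week post vaccine interval".

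**The concern.** Protocol 4.3 explains that the limits on prior therapy are there to reduce immunosuppression risk and to keep earlier immunosuppressants from confounding the results. As anchored, the criteria work in reverse: they require exclusion for exposures further from the first dose and leave the nearest ones to discretion.

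The main stake is safety. A live vaccine could be given in screening to a subject taking prednisone at up to 60 mg/day early in the window and 20 mg/day at its end, who then receives methylprednisolone premedication and, if so randomized, a B-cell-depleting antibody. The protocol itself prompts vaccination near entry: 7.5 and footnote b ask that patients be up to date, without separating live from inactivated vaccines.

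The second stake is interpretation. Under SAP 3.4.4, a DMARD stopped the day before dosing is a prior medication, summarized descriptively. Such exposure precedes treatment assignment and could occur in either arm, so no directional bias is claimed.

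**Working it through.** The plan gives no figure on this point. The 39 flares and 160 subjects in Protocol 9.3 do not depend on it.

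**Step 1: inputs.**
- Look-backs L (Protocol 5.2): 14 days for live vaccines, 28 days for DMARDs, 6 months for biologics. I take 6 months as 183 days, the convention in SAP 3.1; the eligibility text does not define it.
- Screening length s: up to 28 days (6.2.1). It is 21 to 28 days for a subject who starts GC at consent, because inclusion 5 requires at least 3 weeks of GC before randomization. It can be shorter for a subject already on GC at consent.

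**Step 2: formula.** Let d be the number of days before Day 1 on which the product was given. The look-back excludes when s + 1 ≤ d ≤ s + L. The 7.5.1 list applies from Day 1 onward. Neither rule applies when 1 ≤ d ≤ s.

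**Step 3: results, in days before Day 1.**

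| Product | Excluded, s = 21 | Excluded, s = 28 | Not excluded |
|---|---|---|---|
| Live vaccine (L = 14) | 22 to 35 | 29 to 42 | 1 to s |
| DMARD (L = 28) | 22 to 49 | 29 to 56 | 1 to s |
| Biologic (L = 183) | 22 to 204 | 29 to 211 | 1 to s (depleter: only after the B-cell sample) |

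The upper limits at s = 28 are 14 + 28 = 42, 28 + 28 = 56 and 183 + 28 = 211.

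**Step 4: does another rule close the gap?**
- *Pre-infusion check (7.1.1.4).* It leads to 6.4.1 item 12, which takes its scope from 7.5.1, and that list is confined to the RCP and OLP.
- *Day 1 eligibility verification (Table 4).* It re-applies the same wording.
- *Exclusion 1.* It depends on investigator judgement about a condition.
- *Table 3 footnote b.* It acts only when a physician advises delay, and its stated reason is vaccine response.
- *Exclusion 19.* The CD19+ count catches a depleter given before the screening sample, not after it.
- *Exclusion 24.* It covers participation in other trials, not marketed products.
- *Drugs continued past Day 1.* These are already prohibited, so the gap concerns exposure confined to screening.

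**Step 5: comparison within the protocol.** Exclusion 23 (active infection) is anchored at randomization. OLP entry (6.2.3.1 item 3 and Table 5 footnote a) requires a 28-day washout of non-GC immunosuppressants before OLP Dose 1. Nothing similar precedes RCP Dose 1.

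**Step 6: exclusions with the same kind of anchor that need no change.** Exclusion 8 (investigational agents) is largely covered by exclusion 24. Exclusion 15 (opportunistic infection) is largely covered by exclusion 23 and the 6.4.1 check.

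**The case against.** The best counter-argument is that item 12 of 6.4.1 has no time limit of its own. Read as covering only receipt after Day 1, it has almost nothing to check before the first infusion, so a sensible site would look back. The RCP start cited here also comes from a definition of an analysis window, and Table 4 places the Visit 2 eligibility and medication checks inside the RCP. This does not close the gap. Item 12 refers expressly to 7.5.1, whose list names the RCP and OLP. Starting the RCP with the Visit 2 procedures would cover at most Day 1 itself, not the preceding weeks.

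A second argument is that the realistic cases are already handled. Exclusion 1 addresses these harms, vaccination history and medications are reviewed at screening, and flare treatment in screening is specified as GC. A DMARD would have to be started after consent and stopped before Day 1, and a depleter would have to follow the B-cell sample. That fairly describes the likelihood. The depleter case is remote and the live vaccine case is the strongest. But these safeguards rest on discretion or circumstance, and sites may apply them differently.

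A third argument is that the safety scenario should not pair 60 mg/day with a vaccine given the day before dosing, since subjects must be at 20 mg/day the day before randomization. That is correct: the higher dose can apply only earlier in screening.

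Finally, no effect is demonstrated. That stands: the day counts measure the gap in the rule, not risk.

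**Conclusion.** The concern holds. On the protocol's wording, no mandatory criterion bars a live vaccine, a DMARD or a non-depleting biologic given only between consent and Day 1, or a B-cell depleter given in that time after the screening B-cell sample. The open window is up to 28 days, and 21 to 28 days for subjects who start GC at consent. At the maximum, the furthest exposure that excludes and the nearest that does not are 42 versus 1 day for live vaccines, 56 versus 1 for DMARDs and about 211 versus 1 for biologics.

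The conclusion rests on screening starting at consent, as 6.3.1.1 states, and on 7.5.1 meaning what it says about its scope; the 211 also rests on the 183-day reading of 6 months. Confidence in the reading of the text is high. How often such exposures occur is unknown, and no event count, sample size or power figure changes. This is a safety and eligibility point that should be corrected because it is cheap to close, not one that undermines the primary analysis.

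**What to change.** 1. In exclusions 5, 6, 7 and 10, keep each look-back and add *or at any time between screening and Day 1*, so that the criteria meet the start of the 7.5.1 period.
2. In Table 3 footnote b, state that live vaccines may not be given during screening, and that a subject who receives one is screen-failed and may be rescreened.
3. Confirm both at the existing Day 1 eligibility step in Table 4.
4. Leave exclusions 8 and 15 as they are.

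The cost is amendment wording. Concomitant medications are already recorded at screening and Day 1, so no new data are needed.

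The downside is that a few subjects would need rescreening (allowed once, 5.3) and some would be lost for the current flare, because inclusion 5 limits GC to 4 weeks before consent and 8 weeks before randomization. As an example, take a subject on GC since first consent who must sign a new one. A live vaccine on day v means v + 14 days of GC by then, so v can be at most 14 if GC is to stay within 28 days. For a DMARD the sum is v + 28, which leaves no room. Protocol 10.3 allows rescreening within 30 days under the signed consent, which may ease this for some.
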